10.5.1 Efficacy Analyses

The primary and key secondary efficacy analyses that compare ZX008 to placebo will be performed using subjects from Cohort 2 only. Efficacy endpoints, such as convulsive seizure frequency, assessed in Cohort 1 during the Transition Period will be summarized with descriptive statistics only.

10.5.1.1 Primary Efficacy Analysis – Cohort 2

The primary efficacy endpoint is the change in the mean convulsive seizure frequency (MCSF) per 28 days between the Baseline and T + M periods. The MCSF will be calculated from all available data collected during the Baseline or T + M Periods.

The primary endpoint will be analyzed using an analysis of covariance (ANCOVA) model with treatment group (ZX008 or placebo) and age group (< 6 years, \geq 6 years) as factors, and with baseline frequency as a covariate. The primary analysis will compare the ZX008 group to the placebo group using a two-sided test at the $\alpha=0.05$ level of significance.

Since the ANCOVA used in the primary analysis relies on assumptions of normality, the primary endpoint will also be analyzed using a nonparametric method that does not require as stringent assumptions. A nonparametric test will be used to compare the ZX008 group to the placebo group while stratifying for age group. If normality assumptions are not met, the results of the nonparametric test will be used to assess the primary objective.

Additional analyses will compare the percentage changes between the baseline MCSF and the MCSF measured independently during the Titration Period alone and the Maintenance Period alone.

10.5.1.2 Key Secondary Analyses – Cohort 2

The first key secondary endpoint – the proportion of subjects who achieve a $\geq 50\%$ reduction from baseline in convulsive seizure frequency – is derived directly from the primary endpoint. That is, the proportion of subjects in the ZX008 group who have a change in convulsive

frequency of at least 50 percentage points will be compared to the analogous proportion in the placebo group. The comparison will be made using a logistic regression model that incorporates the same factors and covariates as the ANCOVA used in the primary analysis. The analyses will be performed using data collected over the T + M period.

The longest interval between convulsive seizures will be calculated for each subject over the entire T + M period. The ZX008 and placebo groups will be compared using a Wilcoxon test.

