6.1.2 Multiplicity Strategy and Testing Hierarchy

The multiplicity issues in the statistical inference in this study arise from multiple endpoints.

The efficacy analyses will employ a serial gatekeeper strategy to maintain the Type 1 error rate at $\alpha = 0.05$ across the family of analyses that support the primary and key secondary objectives.

All statistical analyses will be performed and results tabulated with test statistics, p-values, and/or 95% confidence intervals.

Formal statistical testing will be performed for one primary endpoint and two key secondary endpoints for the comparison of ZX008 0.5 mg/kg with Placebo. In order to preserve the overall Type 1 error rate at $\alpha = 0.05$, these tests will proceed as follows:

Step 1: The primary efficacy endpoint (mean convulsive seizure frequency per 28 days) will be formally tested first between the ZX008 0.5 mg/kg and Placebo group. If the comparison is statistically significant at $\alpha = 0.05$ (2-sided) level, the hypothesis testing will proceed to Step 2. Otherwise formal testing of the other hypotheses stops.

Step 2: The secondary efficacy endpoint (proportion of subjects who achieve a $\geq 50\%$ reduction from baseline in convulsive seizure frequency) will be compared between the ZX008 and Placebo

group. If the comparison is statistically significant at $\alpha = 0.05$ (2-sided) level, hypothesis testing will proceed to Step 3. Otherwise formal testing of the other hypotheses stops.

Step 3: The endpoint longest convulsive seizure-free interval endpoint will be compared between ZX008 and Placebo using a significance level of $\alpha = 0.05$ (2-sided).

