6.3.1.1 Primary Analysis Tests

T + M Period:

The primary analysis will compare the ZX008 0.5 mg/kg/day group to the placebo group using a two-sided test at $\alpha = 0.05$ level of significance.

The primary endpoint (CSF_{T+M}) will be analyzed using an analysis of covariance (ANCOVA) model with treatment group (ZX008 or Placebo) and age group (< 6 years, ≥ 6 years) as

classification factors, log baseline frequency (CSF_B) as a covariate in the model, and log CSF_{T+M} as response. Treatment group means and the difference from placebo will be estimated with least squares means from the analysis model along with 95% confidence intervals and associated 2-sided p-values. Estimated treatment group means and CI endpoints will be exponentiated for presentation.

The null hypothesis

$$H_0: \mu_{Z008} - \mu_P = 0,$$

will be tested against the alternative

$$H_A: \mu_{Z008} - \mu_P \neq 0,$$

where μ_{Z008} and μ_P represent the ZX008 0.5 mg/kg and Placebo group means (on the log scale), respectively.

Rejection of the null hypothesis in favor of the alternative, in the presence of a statistically significantly bigger reduction in mean convulsive seizure frequency from baseline for the treatment group compared to the placebo group, (two-sided p-value < 0.05) will be regarded as evidence of a treatment benefit in favor of ZX008 0.5 mg/kg group.

Sample SAS code for the ANCOVA described above is as follows:

```
proc glm data=temp;
  class agegrp trtp;
  model csftm = bcsf agegrp trtp / SS3;
  lsmeans trtp / pdiff stderr;
```

where trtp = randomized treatment group (with codes 1, 2 indicating placebo, and 0.5 mg groups).

bcsf = log(CSF_B),
csftm = log(CSF_{T+M})
agegrp = age group.

Additional statements may be used to obtain estimates and 95% confidence interval. Endpoints of the CIs may be exponentiated to obtain CI on the original scale. Fitted values and residuals may be plotted to check model assumptions.

Since the ANCOVA used in the primary analysis relies on assumptions of normality, the primary endpoint will also be analyzed using a nonparametric method that does not require as stringent assumptions. A nonparametric ANCOVA will be used to analyze the data, with ranks of the baseline CSF_B as a covariate and ranks of CSF_{T+M} as response. If normality assumptions are not met, the results of the nonparametric test will be used to assess the primary objective.

Treatment by Baseline Seizure Category:

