6.3.2 Key Secondary Analyses

6.3.2.1 Proportion of subjects with ≥50% Reduction from Baseline in Convulsive Seizure Frequency (50% Responder Rate)

Subjects with a percent reduction in convulsive seizures of at least 50 percentage points from baseline will be identified and the overall proportion within each treatment tabulated. That is, the proportion of subjects in the ZX008 0.5 mg/kg/day group who have a decrease in convulsive

frequency of at least 50 percentage points will be compared to the analogous proportion in the placebo group.

The comparison between ZX800 treatment group and Placebo group will be made using a logistic regression model that incorporates the same factors as the ANCOVA used in the primary analysis. This will model a categorical response variable (achieved at least a 50 percentage point reduction, yes or no) as a function of treatment (ZX008 and placebo), baseline seizure frequency and age group (< 6 years, \geq 6 years).

Descriptive statistics will be presented by treatment group, and will include the number and proportion of subjects < 6 years, \geq 6 years, and overall achieving the reduction along with the model estimated odds ratio (including a 95% confidence interval) and p-value for comparison of ZX008 0.5 mg/kg/day to placebo.

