6.3.2.3 Longest Convulsive Seizure-Free Interval

The longest interval between convulsive seizures will be analyzed.

For each subject, the longest interval between convulsive seizures will be calculated over the entire T+M period. This will be derived as the maximum of the number of days between consecutive convulsive seizures. The intervals between consecutive convulsive seizures will be calculated as below, after which the longest interval between convulsive seizures will be derived.

If a subject has two consecutive days of missing diary data, the end of the current seizure-free interval will be the first date of missing diary data, and a new one begun on the next date that diary data are available and no seizure occurs [In that case, for purpose of calculation of this variable, all intervening days, after the 2nd day, with missing diary data, will be assumed to have a convulsive seizure occurrence, until the first available date with non missing diary data.]

Let Date0 (=Day1) be the first day of treatment. If convulsive seizure occurs on five days having dates as Date1, Date2, Date3, Date4 and Date5, where

Date5>Date4>Date3>Date2>Date1 \geq Date0, and let LDT = Last date of treatment in the maintenance period, where LDT \geq Date5, then the time interval between convulsive seizures will be calculated as follows:

I1=Date2 - Date1

CONFIDENTIAL

Final 25 June 2018

I2=Date3 - Date2

I3=Date4 – Date3,

I4=Date5 – Date4.

For completeness, we calculate the time to the first seizure as

I0=Date1 – Date0,

and the time from the last seizure to end of treatment as

I5 = LDT – Date5.

Here the duration of the longest interval =Maximum (I0, I1, I2, I3, I4, I5).

If the subject does not experience a seizure during treatment, then the last available diary date will be used to compute the duration of the longest interval as follows:

The longest interval=last available diary date – Date0

The median time of the longest convulsive seizure-free interval will be presented. Additional summary statistics will be presented, including mean, minimum, maximum, the 25th and 75th percentiles, 95% confidence intervals on the difference in medians between groups (Hodges-Lehman estimator).

The Wilcoxon rank sum test will be used to test for differences between ZX800 and placebo, and the p-value from this test will be presented. Boxplots of the longest interval data will accompany all descriptive statistics and all data will be provided in a data listing.

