6.3.3 Additional Secondary Endpoint Analyses

6.3.3.1 Number of Convulsive Seizure Free Days

Convulsive seizure free days will be taken from the parent/caregiver diary data.

A convulsive seizure free day will be defined as a day for which diary data are available and no convulsive seizures have been reported. The total number of convulsive seizure free days will be summed for the entire T+M period and similarly for the baseline period.

Seizure free days per 28 days at baseline = (number of seizure free days during baseline)*28/(number of days during baseline with non-missing diary data)

Seizure free days per 28 days during T+M Period = (number of seizure free days during T+M Period)*28/(number of days during T+M Period with non-missing diary data)

The ZX008 treatment group will be compared to the placebo on the number of seizure free days per 28 days during T + M using a similar approach as the primary analysis incorporating the baseline seizure-free frequency as a covariate.

6.3.3.2 Responder Analyses: Proportion with ≥ 25 , or 75% Reduction from Baseline in Convulsive Seizure Frequency

A step-function response curve will be generated for the mITT population. This graph will plot the % of subjects (y-axis) against percentage reduction in seizure frequency per 28 days in the T+M period (x-axis). The horizontal axis will be the % reduction, and the vertical axis will be the % of subjects achieving \geq that % reduction. In the graph, subjects experiencing an increase or no decrease in seizure frequency (i.e., ≤ 0 % reduction) will be regarded as having a 0% reduction in seizure frequency. Hence the ordinate for the 0 time point may not necessarily be at 100%. For example, if 15% of subjects have no reduction in seizure frequency during T+M period compared to the baseline period, the graph will start on the y-axis at 85%. The graph will be generated for all subjects, by treatment group.

- The proportion achieving a $\geq 25\%$ reduction from baseline in convulsive seizures will be analyzed using the same method employed for the $\geq 50\%$ reduction from baseline endpoint.
- The proportion achieving a $\geq 75\%$ reduction from baseline in convulsive seizures will be analyzed using the same method employed for the $\geq 50\%$ reduction from baseline endpoint.

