6.3.3.6 Incidence of Rescue Medication Usage

Use of rescue medication is recorded on the daily diary. In the event of prolonged seizures or status epilepticus, rescue medication is administered according to each subject's personalized regimen consisting of one or more medications. If the first rescue administration does not control the seizures, a second or even third round might be administered. The second and third round might use medications or doses different from the first round of rescue meds.

Rescue medication will be summarized by treatment group and by active treatment vs. Placebo for the following:

- The number of days rescue medication was taken (normalized to 28 days) will be summarized for the T + M period by the mean, standard deviation (SD), median and range. The ZX008 treatment group will be compared to the placebo group using a rank ANCOVA analogous to that described in [Section 6.3.1.1](#). Specifically, the ANCOVA will use ranks of rescue medication frequency during T+M as the response, and will incorporate treatment group as a classification factor and the ranks of rescue medication frequency during Baseline as a covariate.

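### The Step 3 test of the longest convulsive seizure-free interval is valid but ignores baseline seizure frequency, which gives up power that a rank ANCOVA on data already collected would recover

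*SAP*

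**What the plan says.** SAP 6.1.2 sets a fixed sequence at two-sided 0.05: change in convulsive seizure frequency, then the 50% responder rate, then the longest convulsive seizure-free interval. After Step 2, if significant, "hypothesis testing will proceed to Step 3. Otherwise formal testing of the other hypotheses stops".

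- **Step 1** (SAP 6.3.1.1): ANCOVA with treatment and age group as factors and "log baseline frequency (CSF_B) as a covariate in the model". The nonparametric fallback there is an ANCOVA on ranks, with ranked baseline frequency (CSF_B) as covariate.
- **Step 2** (SAP 6.3.2.1): a "logistic regression model that incorporates the same factors as the ANCOVA used in the primary analysis", with baseline seizure frequency and age group in the model.
- **Step 3** (SAP 6.3.2.3): "The Wilcoxon rank sum test will be used to test for differences between ZX800 and placebo". Protocol 10.5.1.2 agrees: "The ZX008 and placebo groups will be compared using a Wilcoxon test". The accompanying estimate is "95% confidence intervals on the difference in medians between groups (Hodges-Lehman estimator").

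Some endpoints outside the hierarchy are also adjusted, each for its own baseline. Seizure-free days are compared "using a similar approach as the primary analysis incorporating the baseline seizure-free frequency as a covariate" (SAP 6.3.3.1). For rescue-medication days, the ZX008 group "will be compared to the placebo group using a rank ANCOVA analogous to that described in" the primary-analysis section (SAP 6.3.3.6). SAP 6.9 records that the Wilcoxon test replaced a log-rank test. It gives no reason for leaving baseline out, and neither document states a power for Step 3.

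**The concern.** A child who has frequent convulsive seizures at baseline will tend to have a short longest interval on either arm. Protocol 4.3 sets a floor on baseline seizures (at least 6 in six weeks) and no ceiling. SAP 6.3.1.1 uses baseline categories running from under 10 to over 50 per 28 days, so it allows for children who differ widely. An unadjusted rank test leaves that predictable variation in the error term.

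What is at stake is the chance of the third formal claim. Of the three alpha-controlled tests, this is the only one that uses no baseline information, although CSF_B is already derived for each child for the primary endpoint.

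**Working it through.** **1. The plan's own figure.** With n per arm = 2(1.960 + 1.282)² SD² / 40²:
- SD 55 (SAP 6.1.10): 39.7, so 40 per arm; power 90.2%.
- SD 58 (protocol 10.1): 44.2, so 45 per arm; power 90.5%.

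Both reproduce. They concern the primary endpoint only, so Step 3 was examined by simulation at both sample sizes.

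**2. Inputs.** From the documents: 1:1 allocation, 42-day baseline, 105-day T+M period, the entry rule in protocol 4.3, the interval rule in SAP 6.3.2.3, and two-sided 0.05 at each step. Assumed, because the documents do not give them: rate ratio 0.5 or 0.6, log-normal baseline rates with a chosen between-child log SD, variation in response (log SD 0.5), over-dispersed daily counts, and full effect from Day 1. The log ANCOVA used log(CSF + 1) so that zeros could be logged.

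**3. Probability that Steps 1, 2 and 3 all succeed** (1000 trials per cell; Wilcoxon → ANCOVA on ranks with ranked CSF_B; gain in points):

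| Per arm, rate ratio | log SD 0.4 | log SD 0.6 | log SD 0.9 |
|---|---|---|---|
| 40, 0.5 | 92.6 → 94.4 (1.8) | 86.9 → 93.7 (6.8) | 78.6 → 93.3 (14.7) |
| 40, 0.6 | 65.3 → 68.4 (3.1) | 58.9 → 69.4 (10.5) | 47.2 → 66.4 (19.2) |
| 45, 0.5 | 94.5 → 96.4 (1.9) | 92.9 → 97.4 (4.5) | 84.7 → 97.1 (12.4) |
| 45, 0.6 | 72.2 → 76.0 (3.8) | 62.1 → 72.7 (10.6) | 52.3 → 74.2 (21.9) |

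The table has no dropout. With 12% early dropout at log SD 0.9 the gains were 14.8 to 18.9. The SD of percentage change was 34 to 49 on active and 67 to 91 on placebo. Pooled as √((a² + b²)/2), that is 54 to 71.

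**4. Closed-form check of Step 3 alone.** If r is the rank correlation between baseline and outcome, adjustment divides the noncentrality by √(1 − r²). At 40 per arm and rate ratio 0.6:
- log SD 0.4: Wilcoxon power 76.3%, r = −0.32. (1.960 + 0.716)/0.947 = 2.82, giving power 80.6% (simulated 81.3%).
- log SD 0.6: 69.0%, r = −0.51. 2.456/0.860 = 2.86, giving 81.5% (simulated 82.2%).
- log SD 0.9: 53.9%, r = −0.65. 2.058/0.760 = 2.71, giving 77.3% (simulated 77.8%).

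The gain therefore comes from the correlation, and the baseline spread drives the correlation.

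**5. A second model tuned to the planning figures.** Settings: difference 40 points, SD 58 at 45 per arm or 55 at 40 per arm, placebo change 0 or −13%, Poisson counts, 10% dropout, age group in the rank ANCOVA, 3000 trials per cell. Joint success by log SD:

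| Per arm, placebo change | 0.6 | 0.8 | 1.0 |
|---|---|---|---|
| 45, 0 | 66 → 77 | 57 → 77 | 49 → 76 |
| 45, −13% | 76 → 84 | 69 → 84 | 61 → 83 |
| 40, 0 | 62 → 75 | 52 → 74 | 46 → 74 |
| 40, −13% | 72 → 82 | 66 → 83 | 59 → 83 |

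Gains are 8 to 13 points at log SD 0.6 and 15 to 28 at 0.8 to 1.0. The same model was then run at narrower spread (rate ratio 0.54, placebo −13%, pooled SD 56 to 57, 700 trials per cell). Gains at log SD 0.3 and 0.4 were 1.6 and 2.9 points at 40 per arm, and 1.6 and 3.6 at 45 per arm. A further run at SD about 54 to 59 gave 2 to 5 points at log SD 0.3 to 0.4, 7 to 11 at 0.6 and 20 to 26 at 0.8 to 1.0.

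**6. Validity and the large-effect limit.** With no effect (7 settings, 1500 trials each), the Wilcoxon test rejected in 3.9 to 6.1% and the rank ANCOVA in 4.1 to 5.9%. Both fit 5% within simulation error. At rate ratio 0.35 the joint gain was 0 to 2 points.

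**The case against.** The plan contains no mistake here. The Wilcoxon test is valid, protocol and SAP agree on it, and it was a deliberate replacement for the log-rank test. It pairs naturally with the Hodges-Lehmann interval, which reports the effect in days, and a sponsor may reasonably prefer that coherence to power. Step 3 is last, is reached only after two successes, and a miss blocks nothing. No baseline longest interval is defined, so the covariate would have to be a different variable. The simulations also assume full effect from Day 1, although the first 21 of the 105 days are titration.

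All of this stands as a limit on importance. It does not remove the point. The Hodges-Lehmann interval can be kept as the estimate, CSF_B is already derived, and ranked CSF_B is already the covariate in the SAP's primary fallback. In the scenarios examined with rate ratios of 0.5 to 0.6, the adjusted test had the higher joint probability each time.

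Two stronger readings are tempting. A reader who tunes a model to the planned SD of 55 to 58 might infer that the gain must be at least 8 or 9 points, and that smaller gains belong to a noisier trial than planned. That holds only if log SDs of 0.6 and above are tried. At the same planned SD, a narrow baseline spread gives gains of about 2 to 5 points. At the other end, one setting with log SD 1.2 and little variation in response gave 43.5 points. Its SDs of 26 and 47 pool to √((26² + 47²)/2) = 38, well below the planning figures.

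**Conclusion.** The point holds as a loss of efficiency in a valid test. It is worth considering, not a defect that must be corrected. Under assumed rate ratios of about 0.5 to 0.6, the joint probability that all three steps succeed rises by about 1 to 5 points at log SD 0.3 to 0.4, roughly 5 to 13 at 0.6 and about 15 to 28 at 0.8 to 1.0. Two cells at log SD 0.9 with rate ratio 0.5 fell slightly below that last range, at 12.4 and 14.7. The gain is near zero if the true effect is very large.

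These are joint probabilities, not probabilities conditional on passing Steps 1 and 2. All are illustrative: the documents give no effect size or correlation for this endpoint and no spread of baseline rates. The direction is firm; the size is not. The protocol and SAP differ on sample size (45 and 40 per arm), but the conclusion is the same at either.

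**What to change.** Before unblinding, amend SAP 6.3.2.3 so that the Step 3 test is a rank ANCOVA: ranks of the longest interval as response, treatment and age group as factors, rank of CSF_B as covariate. Keep the Wilcoxon test and the Hodges-Lehmann interval as supportive, and state that the Step 3 p-value may not agree exactly with that interval. List the change in SAP 6.9, because protocol 10.5.1.2 also names the Wilcoxon test.

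The cost is SAP wording and a small programming change, with no new data. The covariate and the age term must be written out, because the rank ANCOVAs planned for non-convulsive seizures and rescue medication use each endpoint's own baseline and name no age factor. The real downside is that a rank ANCOVA gives no effect in days, so the estimate and the test are no longer exactly paired.

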6.3.3 Additional Secondary Endpoint Analyses

6.3.3.1 Number of Convulsive Seizure Free Days

Convulsive seizure free days will be taken from the parent/caregiver diary data.

A convulsive seizure free day will be defined as a day for which diary data are available and no convulsive seizures have been reported. The total number of convulsive seizure free days will be summed for the entire T+M period and similarly for the baseline period.

Seizure free days per 28 days at baseline = (number of seizure free days during baseline)*28/(number of days during baseline with non-missing diary data)

Seizure free days per 28 days during T+M Period = (number of seizure free days during T+M Period)*28/(number of days during T+M Period with non-missing diary data)

The ZX008 treatment group will be compared to the placebo on the number of seizure free days per 28 days during T + M using a similar approach as the primary analysis incorporating the baseline seizure-free frequency as a covariate.

6.3.3.2 Responder Analyses: Proportion with ≥ 25 , or 75% Reduction from Baseline in Convulsive Seizure Frequency

A step-function response curve will be generated for the mITT population. This graph will plot the % of subjects (y-axis) against percentage reduction in seizure frequency per 28 days in the T+M period (x-axis). The horizontal axis will be the % reduction, and the vertical axis will be the % of subjects achieving \geq that % reduction. In the graph, subjects experiencing an increase or no decrease in seizure frequency (i.e., ≤ 0 % reduction) will be regarded as having a 0% reduction in seizure frequency. Hence the ordinate for the 0 time point may not necessarily be at 100%. For example, if 15% of subjects have no reduction in seizure frequency during T+M period compared to the baseline period, the graph will start on the y-axis at 85%. The graph will be generated for all subjects, by treatment group.

- The proportion achieving a $\geq 25\%$ reduction from baseline in convulsive seizures will be analyzed using the same method employed for the $\geq 50\%$ reduction from baseline endpoint.
- The proportion achieving a $\geq 75\%$ reduction from baseline in convulsive seizures will be analyzed using the same method employed for the $\geq 50\%$ reduction from baseline endpoint.

